## 4. ANALYSIS POPULATIONS

Population	Definition / Criteria	Analyses Evaluated
Infant Safety	
 
• All the infants whose mothers have been randomized and received retosiban or comparator in any of the Phase III treatment trials will be included in the Infant Safety analysis population.
 
• Of these mothers, the Infant Safety population includes the mother/infant pairs who enrolled into the ARIOS study, the mother/infant pairs who decline to consent to the study, and the mother/infant pairs whose fetus/neonates/infants has died prior to the enrolment of the study.
 
• Subjects will be analyzed according to their actual treatment in case this differs from their randomized treatment.
 
	
 
• Disposition
 
• All safety analyses
 

ARIOS Safety	
 
• Subset of the Infant Safety population for which the mother/infant pairs enrolled into the ARIOS study.
 
	
 
• Demographic
 
• All safety analyses
 

Data collected up to and including the 2-year assessments will be included in the descriptive summaries. Data collected beyond the 2-year assessment will be presented, but not included in the summaries.

### 4.1. Protocol Deviations

Protocol deviations are tracked by the study team throughout the conduct of the study in accordance with the Protocol Deviation Management Plan (Reference).

## 5. GENERAL CONSIDERATIONS FOR DATA ANALYSES AND DATA HANDLING CONVENTIONS

### 5.1. Primary Comparisons of Interest

The primary treatment groups are retosiban, placebo, and atosiban.

The primary comparisons between these treatment groups will be:

- Retosiban versus placebo
- Retosiban versus atosiban

### 5.2. Other Comparisons of Interest

A secondary treatment group will include the pooling of placebo and atosiban into a group called “all comparators”. The secondary comparison will be the following:

- Retosiban versus all comparators

### 5.3. Multiplicity Adjustment

There will be no multiplicity adjustment.

[Table 1](#) provides an overview of appendices within the RAP for outlining general considerations for data analyses and data handling conventions.

**Table 1 Overview of Appendices**

Section	Component
10.1	Appendix 1 : Protocol Deviation Definitions
10.2	Appendix 2 : Time and Events
10.3	Appendix 3 : Treatment States and Phases
10.4	Appendix 4 : Data Display Standards & Handling Conventions
10.5	Appendix 5 : Derived and Transformed Data
10.6	Appendix 6 : Premature Withdrawals & Handling of Missing Data
10.7	Appendix 7 : Abbreviations & Trade Marks
10.8	Appendix 8 : List of Data Displays

## 6. STUDY POPULATION ANALYSES

### 6.1. Planned Analyses Overview

All analyses will be based on both populations as defined in Section 4, except where specified.

[Table 2](#) provides an overview of the planned study population analyses, with full details of data displays being presented in [Appendix 8](#): List of Data Displays.

**Table 2 Overview of Planned Study Population Analyses**

Display Type	Data Display's Generated		
	Table	Figure	Listing
Subject Disposition (Infant Safety population, only)			
Subject Disposition	Y		Y
Reasons for Withdrawals	Y		Y
Number of Infants Enrolled at Milestone	Y		
Demography (ARIOS Safety population, only)			
Demographics and Baseline Characteristics	Y		Y
Race & Racial Combinations	Y		Y

**NOTES:**

1. Subject Disposition TLFs will only be created for the Infant Safety population.
2. Demography TLFs will only be created for the ARIOS Safety population
3. Y = Yes display generated

## 6.2. Disposition of Subjects

Analyses of disposition data will be based only on the Infant Safety population as defined in Section 4.

Subject status with respect to study status will be summarized in relation to:

- Enrolled
- Not enrolled
- Died in treatment studies
- Study completion and withdrawal/death

The number and percentage of subjects with the above study status will be reported by treatment group. Reasons for withdrawal will be presented.

Subject status with respect to each study milestone will be summarized in relation to:

- Treated at treatment studies
- Infant consented to ARIOS
- Infant not consented to ARIOS
- Enrolled at ARIOS

The number and percentage of subjects with the above study milestone will be reported by treatment group. The number and percentage of subjects reaching each study milestone after enrolling in ARIOS (infant death, 9 months, 18 months, and 24 months) will be presented.

A completed subject is defined as one who has completed all phases of the study up to and including the 2-year assessment. Note: due to protocol amendment 02 which updated the total study duration to 2 years, some infants may have data collected after the 2-year assessment.

Subject disposition data will also be listed. All disposition summaries will be performed using the Infant Safety population.

## 6.3. Demographic and Baseline Characteristics

Analyses of demographic and baseline characteristics will be based only on the ARIOS Safety population as defined in Section 4.

Continuous variables, such as birth weight (kg), APGAR at 5 minutes after birth, and other baseline characteristics as needed will be summarized using descriptive statistics (mean, standard deviation, median, minimum, and maximum) by treatment group.

The following categorical variables will be summarized by reporting the number and percentage of subjects in each category by treatment group:

- Age of infant at enrollment
- Sex
- Birth weight category (<1 kg, 1 - < 2.5 kg, and >= 2.5 kg)
- Maternal GA at randomization (4 GA strata: 240/7 to 256/7, 260/7 to 276/7, 280/7 to 306/7, and 310/7 to 336/7)
- Infant GA at birth (4 GA strata: 240/7 to 256/7, 260/7 to 276/7, 280/7 to 306/7 and 310/7 to 336/7, 340/7 to 366/7, and 370/7 to 416/7)
- APGAR category at 5 minutes after birth (<7 and >= 7)

Demographic and baseline characteristics data will also be listed. Summaries will be performed using the ARIOS Safety population. Additional baseline characteristics which are not listed above can be included in the final analysis.

Races and racial combinations will be presented in a separate table following GSK race reporting standards.

All demographic and baseline characteristics except age of infant at enrollment stated above will be obtained from Phase III SPTL treatment studies.

Age of infant at enrollment is calculated in months between the date of birth and the date of enrollment in ARIOS study.

#### **6.4. Medical Conditions (Current/Past)**

Analyses of medical conditions (current/past) will be based on both populations as defined in Section 4, except where specified.

The number and percentages of subjects with newly diagnosed chronic medical conditions (respiratory, neurological, sensory, gastrointestinal, cardiovascular, renal conditions, and growth parameter) will be presented.

In addition, subject level listings of newly diagnosed chronic medical condition will be listed.

## 7. PRIMARY STATISTICAL ANALYSES

### 7.1. Efficacy Analyses

There is no efficacy analysis planned for this study.

### 7.2. Safety Analyses

All safety summaries will be performed for both populations as defined in Section 4. A listing of all safety data will be presented.

The primary objective of the planned analysis will be to use descriptive statistics to describe the safety and morbidity and mortality outcomes of children exposed to treatment during the Phase III SPTL studies investigating retosiban or comparator for the treatment of SPTL up to 24 months chronological age. The endpoints to be descriptively summarized are those described in Section 2.2. Descriptive statistics will be calculated by treatment group and/or time (up to 24 months chronological age), where appropriate.

For binary outcomes, all summary tables will include the number and percentage of subjects with the response/event. All summary tables will include N for each group (i.e., the total number of subjects in each treatment group).

The focus will be on collecting the safety outcomes as defined in the objectives (e.g., death) and serious AEs (SAEs), including congenital anomalies.

Nonserious AEs will not be tracked. All SAEs and safety outcomes will be followed until resolution, stabilization, or loss to follow-up.

#### 7.2.1. Overview of Planned Analyses

The safety analyses will be based on both populations as defined in Section 4.

Table 3 provides an overview of the planned analyses with further details of data displays being presented in Appendix 8: List of Data Displays.

**Table 3      Overview of Planned Safety Analyses**

Endpoints	Observed			
	Summary		Individual	
	T	F	F	L
Newly Diagnosed Chronic Medical Condition	Y			Y
Adverse Events (AE)				
Serious Adverse Events	Y			Y
Death				Y
Infant Congenital Anomalies	Y			
Infant Neurodevelopment Assessments	Y			Y

Endpoints	Observed			
	Summary		Individual	
	T	F	F	L
Infant Neurodevelopment Impairment	Y			Y
Infant Hospital Utilization				Y

**NOTES :**

- T = Table, F = Figure, L = Listing, Y = Yes display generated.
- Stats Analysis = Represents TFL related to any formal statistical analyses (i.e. modelling) conducted.
- Summary = Represents TFL related to any summaries (i.e. descriptive statistics) of the observed raw data.
- Individual = Represents FL related to any displays of individual subject observed raw data.

## 7.2.2. Adverse Events

Nonserious AEs will not be tracked.

### 7.2.2.1. Serious Adverse Events

SAEs will be coded using the Medical Dictionary for Regulatory Activities (MedDRA) coding dictionary. A mapping of the MedDRA primary system organ class (SOC) and preferred term (PT) that each verbatim term has been coded to will be provided in a listing. In general, SAEs will be presented in descending order from the SOC with the highest total incidence (that is, summed across all treatment groups) for any adverse event within the class to the SOC with the lowest total incidence. Within the SOC level, SAEs will be presented in descending order from the PT with the highest total incidence to the PT with the lowest total incidence. If the total incidence for any two or more PTs within an SOC is equal, the PTs will be presented in alphabetical order. A PT will not be presented if no adverse events occur within the level. At each level of summarization, a subject is counted only once if the subject reported one or more events.

The seriousness of an AE should be assessed by the Investigator independently from the severity of the AE. An SAE is defined as any untoward medical occurrence that at any dose results in death, is life-threatening, requires hospitalization or prolongation of existing hospitalization, results in disability/incapacity, or is a congenital anomaly/birth defect.

Important medical events that may not result in death, be life-threatening, or require hospitalization may be considered SAEs when, based upon medical judgment, they may jeopardize the subject and may require medical or surgical intervention to prevent one of the outcomes listed above.

The number and percentage of subjects with any SAEs occurred before subjects reach 24 months chronological age will be summarized by treatment group in the tables. Within each group, SAEs will be summarized by frequency and proportion of total subjects, by event type, and by category of body system. A listing of SAEs will be provided.

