4.4. Withdrawal Criteria

A child may be withdrawn from the study due to loss to follow-up or if the child's parent/legal guardian voluntarily withdraws consent. All data collected up to the time of withdrawal will be included in the analysis. If a parent/legal guardian fails to complete an assessment, but wishes to remain in the study, they will be allowed to continue by completing future assessments.

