6.2.11. Time Period and Frequency of Detecting SAEs

The RCC-PI or RCC site staff is responsible for detecting, documenting, and reporting events that meet the definition of an SAE.

Child SAEs will be collected from after 28 days post EDD until 24 months chronological age. All SAEs will be reported to GSK/PPD within 24 hours, as indicated in Section [6.2.12](#).

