7.1.2. Loss to Follow-Up

Children for whom follow-up information is never obtained will be considered lost to follow-up. These cases will be tallied in the applicable sections of the study reports. All other cases with some follow-up data will be analyzed up to the length of child follow-up.

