8.3.5.1.2. Serious Adverse Events

Serious AEs as described in Section 6.2.7.2 will be coded using MedDRA and grouped by body system. Serious AEs will be summarized by treatment group as described in Section 8.3.3. Within each group, SAEs will be summarized by frequency and proportion of total subjects, by event type, and by category of body system. Separate summaries will be given for all SAEs, drug-related SAEs, and SAEs leading to withdrawal. Where appropriate, SAEs by month will be tabulated separately.

Full details of all safety analyses will be provided in either the final protocol and/or RAP.

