Due to the early termination of 200719 and 200721, the sample size of ARIOS is small with a total of 98 babies enrolled (6 placebo treated subjects from NB-1, 43 atosiban treated subjects from ZINN and 49 retosiban treated subjects from NEWBORN-1 and ZINN). This represents just 8% of the planned 1230 infants that were to be enrolled in the study. The intent of the design of ARIOS was to compare data from the retosiban exposed group in each of the treatment trials to the placebo exposed group. In order to accomplish this, data from both 200719 and 200721 were to be pooled from all the babies exposed to retosiban and compared against placebo-exposed babies. As there were only 6 babies exposed to placebo with the drop-out rate expected to increase as the study progresses, the sample size will not be sufficient to permit a meaningful comparison of long-term safety between active treatment and placebo subjects if the follow-up study was continued for 5 years of follow-up.

On 28 August 2018, the retosiban IDMC, composed of 1 pediatrician, 2 neonatologists, 2 maternal-fetal medicine specialists and a statistician, confirmed that there were no safety concerns identified following review of ZINN and NEWBORN-1 clinical study reports as well as ARIOS adverse events (including congenital anomalies), neurodevelopment screening assessments (ASQ-3, CBCL/1.5-5, and MCHAT-R/F), and neurodevelopment referrals, from an ARIOS data cut on 15 June 2018, with 34 out of a total of 98 babies having already completed 24 months of safety follow-up. The IDMC also recommended that the neonatal follow-up be limited to 24 months of age given that the small number of enrolled subjects, in particular placebo subjects for comparison, would not yield meaningful results. Twenty-four months, in the IDMC collective opinion, would allow for detection of major neonatal adverse outcomes and safety signals and as such would be sufficient, especially considering that there will be no future development of retosiban.

Furthermore, 24-month outcomes are considered by the experts in the field to be appropriate for safety assessment (Marlow, 2014). [name], who is an IDMC member, in collaboration with regulatory agencies, has developed a manuscript (in press) that recommends that 24-month follow-up is appropriate for safety follow-up in this population.

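### SAE percentages take no account of follow-up, and Table 10.5 keeps never-enrolled infants in the denominator although enrolment differed by arm

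*SAP*

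**What the plan says.** For each treatment group, SAP Section 7.2.2.1 states that "SAEs will be summarized by frequency and proportion of total subjects". Protocol Section 8.3.5.1.2 has the same rule: "Within each group, SAEs will be summarized by frequency and proportion of total subjects, by event type, and by category of body system". SAP Section 7.2 sets N in all summary tables to all subjects in the treatment group.

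Three other parts of the SAP bear on what that percentage means:

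- **Populations (Section 4).** The Infant Safety population includes pairs who declined the follow-up study and pairs whose fetus or infant died before enrolment. The ARIOS Safety population is the enrolled subset.
- **Displays (Section 10.8.3).** The SAE summary is produced for both populations, as Table 10.5 (Infant Safety) and Table 20.5 (ARIOS Safety).
- **Missing data (Section 10.6.2).** Missing safety data are taken to mean that no event occurred.

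The protocol sets the collection window in Section 6.2.11: "Child SAEs will be collected from after 28 days post EDD until 24 months chronological age". Section 8.3.5.1.2 adds a time-resolved display: "Where appropriate, SAEs by month will be tabulated separately". SAP Section 7.2.2.1 and the SAP's list of displays do not contain it. SAP Section 2.1 refers to Section 8 for dropped analyses, but Section 8 does not mention this one.

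**The concern.** A proportion of all subjects estimates the risk over the window only if everyone in N could have had an event recorded throughout it. An infant who never entered the follow-up study cannot contribute a follow-up SAE but still adds one to the denominator of Table 10.5. An enrolled child who leaves early counts as event-free for the rest of the window. Either way, the percentage falls in an arm observed for less time.

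This matters because the study is meant to give assurance about safety, and its two primary comparisons (retosiban with placebo, retosiban with atosiban) will be read from these percentages. If the observed share of infants differs by arm, equal risks will look unequal.

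**Working it through.** **Inputs**

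- Treatment-trial numbers (Protocol Section 1.1.1): NEWBORN-1, retosiban 10 and placebo 13; ZINN, retosiban 50 and atosiban 47.
- Enrolled in the follow-up study (Protocol Appendix 1, Amendment 02 justification): placebo 6, atosiban 43, retosiban 49.
- SAE risk and follow-up by arm are not given. I assume a true risk p of 10% to 40% after 28 days post EDD, equal in all arms.

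**Check of the documents' own figures.** 6 + 43 + 49 = 98, and 98/1230 = 8.0%, as stated. 10 + 13 + 50 + 47 = 120 = 23 + 97, which matches the two trial totals.

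**Step 1: Table 10.5.** If all 120 mothers were dosed and never-enrolled infants count as event-free, the expected percentage is p × enrolled/treated.

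| | Placebo | Atosiban | Retosiban | All comparators |
|---|---|---|---|---|
| Enrolled/treated | 6/13 = 46.2% | 43/47 = 91.5% | 49/60 = 81.7% | 49/60 = 81.7% |
| p = 10% | 4.6% | 9.1% | 8.2% | 8.2% |
| p = 20% | 9.2% | 18.3% | 16.3% | 16.3% |
| p = 30% | 13.8% | 27.4% | 24.5% | 24.5% |
| p = 40% | 18.5% | 36.6% | 32.7% | 32.7% |

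The apparent risk ratio does not depend on p. It is 0.817/0.462 = 1.77 for retosiban against placebo, 0.817/0.915 = 0.89 against atosiban, and 1.00 against all comparators. With no true difference, placebo looks safest and retosiban looks safer than atosiban. In Table 20.5 the never-enrolled infants are removed, and every arm would show p.

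**Step 2: loss among enrolled infants.** Take p = 20% and a constant hazard, h = −ln(0.8) = 0.223 per full follow-up period. If a fraction f leaves halfway, the crude proportion is (1 − f) × 0.20 + f × (1 − √0.8), where 1 − √0.8 = 0.106.

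- f = 0: 20.0%
- f = 30%: 0.140 + 0.032 = 17.2%
- f = 50%: 0.100 + 0.053 = 15.3%

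First events divided by time at risk stays at 0.223 in all three cases. The calculation shows the mechanism only, because no dropout by arm is available.

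**Step 3: window length.** The window starts at a date set by EDD and ends at a date set by birth. It lasts 24 − (16 × 7 + 28)/30.44 = 19.4 months for a birth at 24 weeks and 24 − 28/30.44 = 23.1 months at 40 weeks. A 20% risk over 23.1 months becomes 17.1% over 19.4 months. That contrasts two extreme children. Between arms within each trial, mean times differ as follows:

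- ZINN: 33.71 − 32.51 = 1.2 days = 0.04 months.
- NEWBORN-1: 18.9 − 11.1 = 7.8 days = 0.26 months (to delivery or treatment failure).

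At h = 0.223/23.1 = 0.0097 per month, one month of window moves a 20% risk by about 0.8 × 0.0097 = 0.8 percentage points. The two contrasts are therefore worth about 0.03 and 0.2 points.

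**The case against.** **A reader might infer that the SAP contradicts the protocol.** Protocol Section 7.1.2 says "All other cases with some follow-up data will be analyzed up to the length of child follow-up", and the SAP divides by everyone. The documents do not support that reading. The protocol section that governs SAE analysis has the same wording as the SAP. Section 7.1.2 is a rule on which data to use: children with no follow-up are tallied ("Children for whom follow-up information is never obtained will be considered lost to follow-up") and the others contribute what they have. Section 4.4 says the same of withdrawals: "All data collected up to the time of withdrawal will be included in the analysis". Neither section sets a denominator or asks for person-time. At most, Sections 7.1.2 and 8.3.5.1.2 of the protocol sit uneasily together, and the SAP inherits that.

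**A reader might also infer that earlier birth or dropout will make one arm look safer.** This is not shown. Between arms, the window-length effect is well under one percentage point. Its direction is not assured either, because the protocol's background says risk rises as gestation falls, so the infants with the shorter window are those at higher risk. On dropout, the Amendment 02 text does say "with the drop-out rate expected to increase as the study progresses", but it is arguing against a five-year follow-up and gives no split by arm. The only completion figure, 34 of 98 infants at the June 2018 data cut, is not split by arm either.

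**Much is already covered.** Table 20.5 removes never-enrolled infants, SAP Section 6.2 reports by arm the numbers reaching 9, 18 and 24 months, and SAEs in enrolled infants are listed. The study is descriptive and tests no hypothesis. All of this stands and keeps the point small. It does not remove it: Table 20.5 still ignores dropout, the milestone counts adjust no SAE percentage, and Table 10.5 belongs to the population that the SAP names as primary.

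**Conclusion.** The point holds in a limited form. Both documents plan a crude SAE proportion, and no planned SAE summary accounts for follow-up. The documented distortion is in Table 10.5. At an equal true risk of 20%, it would show about 9% for placebo, 18% for atosiban and 16% for retosiban. Retosiban against all comparators is unaffected by enrolment.

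This rests on two assumptions. The first is that all randomized mothers were dosed. The second is that never-enrolled infants appear with no SAE. SAP Section 7.2.2.1 gives only an upper age limit for the events counted, so SAEs from the treatment studies may be included; the dilution would then be smaller, but two observation periods would be mixed. The result does not depend on whether the missing-data rule reaches infants who were never asked, since being in N without a possible follow-up event has the same effect.

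Loss to follow-up among enrolled infants would act in the same direction, by an amount that the documents do not allow us to state. Chance will also be large: at p = 20% the 6 enrolled placebo infants would be expected to yield 6 × 0.2 = 1.2 children with an SAE. This is a worthwhile improvement in presentation, not a threat to the study's validity.

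**What to change.** For SAEs after 28 days post EDD, in Tables 10.5 and 20.5, beside n and %:

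1. Add child-months at risk by treatment group, from 28 days post EDD to the earliest of 24 months chronological age, death or last contact. Give never-enrolled infants zero.
2. Add the rate of children with a first SAE per 100 child-months. For this rate the clock also stops at the first SAE. Counting children rather than events fits the SAP's once-per-subject rule and keeps repeat admissions in one child from dominating.
3. State that Table 20.5 is the main display for these events, and say whether Table 10.5 includes SAEs from the treatment studies.
4. Restore the by-month tabulation, or record in SAP Section 8 why it is dropped.

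The cost is two columns per table and a little programming. It needs birth date, EDD, death date and last contact; if no last-contact date is held, the last completed questionnaire could serve. The rates will be imprecise for placebo, with at most 6 × 23.1 = 139 child-months, and they summarize the window as if the hazard were roughly constant. They should therefore stand beside n and %, not replace them.
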